#### Gender Affirming Hormonal Therapy

All participants randomized to the Immediate Intervention Arm, who wish to initiate hormonal therapy, will be dispensed GAHT at the site, provided through the study. Participants randomized to the Deferred Intervention Arm will be linked to offsite hormonal therapy services for 6 months and then will be eligible to receive GAHT at the site, provided through the study. All participants who are provided GAHT through the study will receive doses and be administered therapy through the site consistent with national/international standards such as the World Professional Association for Transgender Health until study termination.

Participants are not required to accept GAHT to be eligible to participate in the study. All participants can decide to initiate hormonal therapy after enrollment for the Immediate Intervention Arm or at the 6 months visit for the Deferred Intervention Arm, up until, and including, the Week 39 visit. A GAHT initiation visit will be scheduled up to 10 days following the collection of samples for estradiol and total testosterone testing for initiation/re-initiation of GAHT. If a participant decides to initiate hormonal therapy after Week 39 study visit, hormonal therapy will not be provided through the study and the participant will be linked to gender-affirming services.

At any time during the study, a participant may decide to discontinue taking hormonal therapy and continue participation in the study (see Section 6.4.1).

### **5.3 Study Product Formulation, Content, and Storage**

#### PrEP (Truvada®)

FTC/TDF (Truvada®) is a fixed dose combination tablet containing 200 mg of FTC and 300 mg of TDF. FTC/TDF (Truvada®) must be stored at 25°C (77°F), with excursions permitted between 15°C-30°C (59°F-86°F) [see USP Controlled Room Temperature]. FTC/TDF tablets must be stored and dispensed in the original container. Refer to the relevant Package Insert for further information.

#### PrEP (Descovy®)

FTC/TAF (Descovy®) is a fixed dose combination tablet containing 200 mg of FTC and 25 mg of TAF. FTC/TAF (Descovy®) must be stored at 25°C (77°F), with excursions permitted between 15°C-30°C (59°F-86°F) [see USP Controlled Room Temperature]. FTC/TAF must be dispensed in the original container. Refer to the relevant Package Insert for further information

### Gender Affirming Hormonal Therapy

For participants who are eligible to receive GAHT through the study, the site will need to locally source hormonal therapy for dispensation to the participant. All study drugs obtained locally by the site, for GAHT, will be stored in accordance with the manufacturer's recommendations.

## **5.4 Study Product Supply**

### PrEP (Truvada®)

FTC/TDF 200 mg/300 mg (Truvada®) study product tablets are manufactured and provided by Gilead Sciences, Inc. FTC/TDF 200mg/300mg study product will be available through the National Institute of Allergy and Infectious Disease (NIAID) Clinical Research Products Management Center (CRPMC). The site pharmacist can obtain FTC/TDF study product through the CRPMC by following the instructions in the *Pharmacy Guideline and Instructions for DAIDS Clinical Trial Networks* and instructions in the SSP Manual.

### PrEP (Descovy®)

FTC/TAF 200 mg /25 mg (Descovy®) study product tablets are manufactured and provided by Gilead Sciences, Inc. FTC/TAF 200mg/25mg study product will be available through the National Institute of Allergy and Infectious Disease (NIAID) Clinical Research Products Management Center (CRPMC). The site pharmacist can obtain FTC/TAF study product through the CRPMC by following the instructions in the *Pharmacy Guideline and Instructions for DAIDS Clinical Trial Networks* and instructions in the SSP Manual.

### Gender Affirming Hormonal Therapy

The site will locally procure hormonal therapy for dispensation to participants who wish to initiate therapy and as they become eligible to receive therapy through the site.

*NOTE: Any study drug not provided by the study must be a U.S. FDA approved formulation or otherwise comply with the NIAID (DAIDS) policy that outlines the process for authorizing the use of study products not marketed in the U.S. in NIAID (DAIDS)-supported and/or -sponsored clinical trials. This policy is available on the NIAID (DAIDS) website at <https://www.niaid.nih.gov/sites/default/files/NonFDAapprovedProducts.pdf>*

## **5.5 Study Product Accountability**

### PrEP (Truvada® or Descovy®)

A written prescription must be provided to the site pharmacist when a participant initiates FTC/TDF or FTC/TAF study product. The prescription should be written to ensure that the participant has enough study product to last through the next study visit. Study product should be dispensed per written prescription and labeled with a participant-specific label that is in accordance with local pharmacy laws and regulations along with the instructions in the *Pharmacy Guideline and Instructions for DAIDS Clinical Trial Networks*.

The site pharmacist must maintain compete records of all study products received from the NIAID CRPMC and subsequently dispensed to study participants. After the study is completed,

terminated, or site is otherwise instructed by the study sponsor, all unused study product must either be returned to the CRPMC (U.S. sites only), or else destroyed (international sites) in accordance with the relevant procedures provided in the manual *Pharmacy Guideline and Instructions for DAIDS Clinical Trial Networks*.

## **5.6 Adherence Assessments**

PrEP and GAHT adherence data will be collected via self-report at each follow-up visit and through laboratory testing.

### Self-Report

Participants will be asked self-reported questions about adherence to PrEP and GAHT via an electronic Case Report Forms (eCRF) and/or Audio Computer-Assisted Self Interview (ACASI) within the Follow-up Behavioral Questionnaires. Questions will be worded to reduce stigma associated with lack of adherence.

### Biomedical Markers of Adherence

Systemic drug concentrations are reliable and objective markers of adherence. TFV-DP, the intracellular metabolite of TFV, can be measured in red blood cells in dried blood spot (DBS) samples, and provides a longer-term marker of PrEP adherence than measurement of TFV in plasma. As directly observed therapy (DOT) studies have been performed for both FTC/TDF (Truvada®) and FTC/TAF (Descovy®), **TFV-DP measurements in red blood cells (collected on DBS) will be used as the primary indicator of PrEP adherence and persistence.** These data will be used to understand PrEP adherence in study participants. Data on FTC-TP will also be collected in this study. Plasma will also be collected and may be evaluated to understand short-term PrEP adherence, as plasma provides a more granular and narrower window of PrEP-taking behaviors.

Results from testing to assess biomarkers of PrEP adherence will not be returned to the study site or participants.

**In addition to self-report, GAHT use will be evaluated during quarterly visits via the laboratory measurement of total testosterone and estradiol concentrations.**

## **5.7 Toxicity Management**

Toxicity management guidelines can be found in Appendix II (Toxicity Management).

## **5.8 Concomitant and Drug Interactions**

Information regarding drug interactions are found in the Package Inserts for Truvada® and Descovy®. Sites need to ensure they have the most up to date version of the Package Inserts in their study-specific files as well as available for clinical reference.

All concomitant medications/preparations (prescription and non-prescription) including alternative/complementary medications/preparations (e.g., herbs, vitamins, etc.) taken within 30 days prior to enrollment and anytime thereafter during study participation will be collected in the study participant's chart and on applicable study eCRFs. Alcohol and recreational or street drug

use reported by a participant during the study will be recorded in the participant's study chart only (and not captured on the Concomitant Medication log for inclusion in the study database).

Additionally, for all participants, sites will document in eCRFs all GAHT and PrEP agents obtained outside the study site on the applicable study eCRFs.

The CMC should be contacted for any questions regarding coadministration of any of the drugs listed below.

Please note that the Package Inserts for Truvada® or Descovy® do not list any prohibited medications. The drug interaction information listed below comes directly from the Package Insert for each product.

**Truvada® Drug Interaction:**

**Drugs Affecting Renal Function**

Coadministration of Truvada® with drugs that are eliminated by active tubular secretion may increase concentrations of FTC, tenofovir, and/or the coadministered drug. Some examples include, but are not limited to, acyclovir, adefovir dipivoxil, cidofovir, ganciclovir, valacyclovir, valganciclovir, aminoglycosides (e.g., gentamicin), and high-dose or multiple NSAIDs. Drugs that decrease renal function may increase concentrations of FTC and/or tenofovir.

**Established and Other Potentially Significant Interactions**

Established and Significanta Drug Interactions: Alteration in Dose or Regimen May Be Recommended Based on Drug Interaction Trials (Table 7 under section 7.2 of the Truvada® Package Insert)

Concomitant Drug Class: Drug Name	Effect on Concentration	Clinical Comment
NRTI: didanosine c	↑ didanosine	
Patients receiving TRUVADA and didanosine should be monitored closely for didanosine-associated adverse reactions. Discontinue didanosine in patients who develop didanosine-associated adverse reactions. Higher didanosine concentrations could potentiate didanosine-associated adverse reactions, including pancreatitis, and neuropathy. Suppression of CD4+ cell counts has been observed in patients receiving TDF with didanosine 400 mg daily.
 
In patients weighing greater than 60 kg, reduce the didanosine dose to 250 mg when it is coadministered with TRUVADA. Data are not available to recommend a dose adjustment of didanosine for adult or pediatric patients weighing less than 60 kg. When coadministered, TRUVADA and Videx EC may be taken under fasted conditions or with a light meal (less than 400 kcal, 20% fat).

HIV-1 Protease Inhibitors: atazanavir c  lopinavir/ritonavir c atazanavir/ritonavir c darunavir/ritonavir c	↓ atazanavir  ↑ tenofovir	
When coadministered with TRUVADA, atazanavir 300 mg should be given with ritonavir 100 mg.
 
Monitor patients receiving TRUVADA concomitantly with lopinavir/ritonavir, ritonavir-boosted atazanavir, or ritonavir-boosted darunavir for TDF-associated adverse reactions. Discontinue TRUVADA in patients who develop TDF-associated adverse reactions.

Hepatitis C Antiviral Agents: sofosbuvir/velpatasvir c sofosbuvir/velpatasvir/ voxilaprevir c  ledipasvir/sofosbuvir c	↑ tenofovir	
Monitor patients receiving TRUVADA concomitantly with EPCLUSA® (sofosbuvir/velpatasvir) or VOSEVI® (sofosbuvir/velpatasvir/voxilaprevir) for adverse reactions associated with TDF.
 
Monitor patients receiving TRUVADA concomitantly with HARVONI® (ledipasvir/sofosbuvir) without an HIV-1 protease inhibitor/ritonavir or an HIV-1 protease inhibitor/cobicistat combination for adverse reactions associated with TDF. In patients receiving TRUVADA concomitantly with HARVONI and an HIV-1 protease inhibitor/ritonavir or an HIV-1 protease inhibitor/cobicistat combination, consider an alternative HCV or antiretroviral therapy, as the safety of increased tenofovir concentrations in this setting has not been established. If coadministration is necessary, monitor for adverse reactions associated with TDF.

- a. This table is not all inclusive.
- b. ↑=Increase, ↓=Decrease
- c. Indicates that a drug-drug interaction trial was conducted.

### Descovy® Drug Interaction:

#### Drugs Affecting Renal Function

Coadministration of Descovy® with drugs that reduce renal function or compete for active tubular secretion may increase concentrations of FTC, tenofovir, and other renally eliminated drugs and this may increase the risk of adverse reactions. Some examples of drugs that are eliminated by active tubular secretion include, but are not limited to, acyclovir, cidofovir, ganciclovir, valacyclovir, valganciclovir, aminoglycosides (e.g., gentamicin), and high-dose or multiple NSAIDs.

### Established and Other Potentially Significant Interactions

**Established and Other Potentially Significanta Drug Interactions** (Table 5 under section 7.3 of the Descovy® Package Insert)

Concomitant Drug Class: Drug Name	Effect on Concentration b	Clinical Comment
Antiretroviral Agents: Protease Inhibitors (PI)		
tipranavir/ritonavir	↓ TAF	Coadministration with DESCovy is not recommended.
Other Agents		
Anticonvulsants: carbamazepine oxcarbazepine phenobarbital phenytoin	↓ TAF	Consider alternative anticonvulsant.
Antimycobacterials : rifabutin rifampin rifapentine	↓ TAF	Coadministration of DESCovy with rifabutin, rifampin, or rifapentine is not recommended.
Herbal Products: St. John's wort ( Hypericum perforatum )	↓ TAF	Coadministration of DESCovy with St. John's wort is not recommended.

a. This table is not all inclusive.

b. ↓=Decrease

## 6.0 STUDY PROCEDURES

An overview of the study visits and evaluations schedule is provided in Appendix Ia-Ic. Presented in this section is additional information on visit-specific study procedures. Detailed instructions to guide and standardize procedures across sites are provided in the HPTN 091 SSP Manual.

### 6.1 Implementation Testing

A run-in period will be performed by enrolling a small number of participants at each participating site prior to full study rollout. The purpose is to fully capacitate the peer counselors and the clinicians providing integrated clinical services in the intervention.

The run-in period will follow the same study design (refer to Section 3.0) and schedule of events as the full study (refer to Sections 6.2 – 6.4, 6.6 – 6.8, and Appendix Ia – Ic), with the exception of the Qualitative Data Collection sub-study, but with limited enrollment and follow-up. Accordingly, up to 10% of site's target sample size will enroll over a 3-month period, and each participant in this group will be followed until the last participant enrolled as part of the run-in period at the site completes their 6-month follow-up visit. The number enrolled may vary by site. There will not be a separate consent for participants in the run-in period since all study procedures and relevant consent information will be the same independently if they enroll in the Implementation Testing part of the study or the full study, with the exception of the option to participate in the Qualitative Data Collection sub-study. **While the run-in period is ongoing, no additional participants may be enrolled in the protocol.**

The run-in period will allow the study sites an opportunity to optimize local study procedures before the full study proceeds. As such, for each study site participating in the run-in period, a study-conduct review will take place after the last participant enrolled has completed their 6-month follow-up visit. This review will be conducted in part by the HPTN Study Management Committee (HPTN SMC). The review will involve an evaluation of key operational components of the study, such as fidelity to intervention and referral procedures, data management procedures, and laboratory procedures, all in accordance with Good Clinical Practice (GCP). The review may also include evaluation of screening, enrollment, and retention data. Follow-up of the participants enrolled in the run-in period will continue uninterrupted during the time the run-in period is being evaluated. This provides for continuity of study operations at the study sites should the full study proceed.

## **6.2 Screening Visit**

It is the responsibility of the local site to determine the best approach to screening. Multiple screening visits may be conducted, if needed, to complete all required procedures. The screening to enrollment window is 30 days, starting on the day the informed consent form is administered. Written informed consent for screening will be obtained before any screening procedures are initiated. Screening procedures will discontinue once ineligibility is determined for participants who do not meet the eligibility criteria. If a participant does not complete all screening procedures within 30 days of signing the Screening Informed Consent Form (ICF), all screening procedures must be repeated, starting with the informed consent process. Participants may rescreen once at the discretion of the IoR or their designee, and per guidance found in the SSP Manual. Further rescreening for administrative reasons may be permitted with the approval of the CMC.

Sites will follow the HIV testing algorithm for Screening included in the SSP Manual. If a reactive/positive result is obtained for any HIV test, the person is not eligible for the study, even if found to be HIV-uninfected upon confirmation. Additional testing to confirm suspected HIV infection during Screening will be performed in accordance with local guidelines. If HIV infection is confirmed, participants will receive counseling and be referred for appropriate care, as necessary.

Participants must have fasted for at least 8 hours, preferably 12 hours, prior to lipid profile sample collection. Sites should verify that a participant has fasted prior to sample collection. If the patient has not fasted, the specimen should not be collected for lipid profile testing, and the participant should be scheduled to return to the site for sample collection prior to their Enrollment Visit.

Individuals deemed not eligible will be informed that they do not meet the eligibility criteria for the study and will be referred for appropriate medical care, if necessary.

## **6.3 Enrollment Visit**

HIV test results from Screening must be available and reviewed prior to enrollment. If a participant has a reactive test at enrollment, HIV infection should be confirmed on a second sample collected on a date different from the Enrollment visit as per the HIV testing algorithm found in the SSP Manual.

The definition of enrollment in this study is the point of randomization. That is, if a site successfully randomizes a participant in the randomization system, that participant is considered enrolled.

A complete medical history and physical exam will be performed at Screening and should include assessment for acute HIV infection. A symptoms-directed physical exam will be done at the Enrollment Visit prior to enrollment.

For participants initiating GAHT, testing for estradiol and total testosterone will need to be performed prior to hormonal therapy initiation. A GAHT initiation visit will be scheduled up to 10 days following the collection of samples for estradiol and total testosterone testing for initiation/re- initiation of GAHT. This timeframe will allow for sufficient time for sites to receive laboratory results and for participants taking part in the DHI sub-study to complete the DOT phase.

## **6.4 Follow-Up Visits**

Follow-up visits will occur on a quarterly basis at Week 13 (Month 3), Week 26 (Month 6), Week 39 (Month 9), Week 52 (Month 12), Week 65 (Month 15), Week 78 (Month 18) after enrollment, as per Appendix Ia. Mental health assessment will be included as part of the medical and physical history assessment. Specific visit windows are outlined in Section 6.5 of the protocol. Per Section 6.3, participants initiating/re-initiating GAHT will need a GAHT initiation visit up to 10 days after collection of samples for review of baseline endogenous estradiol and testosterone concentrations. See Section 6.4.2 for information on re-initiation procedures.

Fasted samples for lipid profile testing will be collected at Week 26 (Month 6) and Week 78 (Month 18). Prior to sample collection, sites must confirm with participants that they have fasted for at least 8 hours, preferably 12 hours, prior to sample collection. If a participant has not fasted, the sample should not be collected for lipid testing, and the participant should be scheduled to return for sample collection ideally within 72 hours from the visit.

Participants who voluntarily withdraw from the study or are lost to follow-up will be contacted for an interview to explore reasons for no longer participating. These interviews can be conducted either in person or by phone, based on participant's availability and/or preference.

Week 78 (Month 18) will serve as the Termination Visit. Prior to this visit, participants should be linked to local providers for PrEP, hormonal therapy, and/or STI testing and treatment, as needed, per site SOP.

### **6.4.1 Follow Up Procedures for Participants Who Discontinue Study Products**

A participant may discontinue use of PrEP and/or hormonal therapy and remain on study. Product may be held in response to a clinical event or participant-initiated decision. Discontinuation is defined as not using study product for 30 or more days, independently of the rational for study product discontinuation. If this occurs, study visits continue according to the Schedule of Events (SOE) found in Appendix Ia, with the exceptions noted in Tables 4 and 5.

**Table 4: PrEP (held or discontinued)**

Procedure discontinued after product hold	Notes
Provision of PrEP	Participant should return remaining PrEP to the site if PrEP is held or discontinued.
PrEP counseling and support	Any participant who wishes to discontinue PrEP should be counseled on the implications of stopping PrEP, be offered additional risk reduction counseling and (if not during a regular visit where it is already provided) HIV testing.
Adherence and acceptability assessments	Adherence and acceptability assessments related to PrEP will be part of the ACASI. These specific questions will be included at the visit in which PrEP is held and discontinued at subsequent visits when product is not being provided (using a skip pattern).

**Table 5: GAHT (held or discontinued)**

Procedure discontinued after product hold	Notes
Provision of GAHT	Participant should return remaining GAHT to the site if GAHT is held or discontinued.
GAHT counseling and support	Any participant who wishes to discontinue GAHT should be counseled on the clinical implications of stopping GAHT.
Estradiol and total testosterone testing	Hormonal monitoring and testing should be completed at the visit in which GAHT is held and discontinued at subsequent visits when GAHT is not being provided.
Adherence and acceptability assessments	Adherence and acceptability assessments related to GAHT will be part of the ACASI. These specific questions will be included at the visit in which GAHT is held and discontinued at subsequent visits when product is not being provided (using a skip pattern).

#### 6.4.2 Procedures for Participants who Initiate or Re-initiate Study Products

There are some situations when a participant may initiate or re-initiate product use during follow-up. This includes product being held due to a clinical event or because a participant declines either PrEP or GAHT during follow-up. Re-initiation is defined as restarting study product use after 30 or more days off study product.

Participants who decline PrEP can begin (or reinitiate) PrEP at any time up to and including their Week 39 visit unless contraindicated. At the visit when PrEP is to be initiated or reinitiated, the following procedures should be conducted, and **results should be available prior to PrEP dispensation:**

- Creatinine clearance
- HIV testing
- Fasting lipid profile (for participant reinitiating PrEP, lipid profile is not required if done within six months of product re-initiation)

Participants may begin co-located GAHT any time after enrollment (Immediate Intervention Arm) or after the 6-month visit (Deferred Intervention Arm) up to and including the Week 39 visit unless contraindicated. At the visit when co-located GAHT is to be initiated or reinitiated, the following procedures should be conducted, and **results should be available prior to GAHT dispensation:**

- Estradiol and total testosterone testing

If either product was held due to a clinical event, sites need to assess the event and confirm resolution. This may be done by clinical assessment, medical history, and/or laboratory assessment.

The CMC may be consulted for additional guidance prior to initiation/re-initiation of study product(s).

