Participants who decline PrEP can remain in follow-up (see Section 6.4.1) and can begin PrEP at any time up to and including their Week 39 visit. Enrolling participants who decline PrEP at baseline allows for an assessment of the impact of the intervention on PrEP uptake over time. If a participant has not been provided PrEP on study by Week 39 and decides to initiate PrEP after the Week 39 study visit, PrEP will not be provided at the study site; rather the participant will be linked to local PrEP services (see Section 5.2 for details). Week 39 is the last visit before the end of the first year of the study which will provide information on PrEP uptake. The second year will provide information on PrEP persistence so PrEP cannot be initiated at the site but as noted, participants can be referred.

The multi-component interventional package including GAHT and PHN using SBCM is outlined in Table 3. During the first six months, the Deferred Intervention Arm includes standard HIV prevention interventions such as risk-reduction counseling (Project RESPECT; Prevention Cohort) and provision of PrEP. Participants in the Deferred Intervention Arm will be linked with institutions that have established a partner agreement with the site. A partner agreement at each site will include at a minimum an agreement to provide care to study participants in a timely manner.

Shown in Table 3 is each intervention component, a brief description, the theoretical foundation, and the staff member(s) responsible for component delivery.

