### **5.2 Study Product Administration**

#### PrEP

FTC/TDF 200mg/300mg (Truvada®) or FTC/TAF 200mg/25mg (Descovy®) will be taken as one tablet orally once daily with or without food during the 18 months of study participation.

Participants do not have to accept PrEP to be eligible to participate in the study. A participant can decide to initiate PrEP administration at any time after enrollment up until, and including, the Week 39 study visit. Once initiated, the study participant may also decide to discontinue taking PrEP at any time during the 18 months of study participation. A participant can reinitiate PrEP after discontinuation up to, and including, Week 65 of study participation. If a participant requests to reinitiate PrEP at site after discontinuation and had originally initiated PrEP use at site by Week 39 of study participation, the participant is eligible to receive PrEP provided by the study at the site. If a participant has not been provided PrEP at the site by Week 39 and decides to

initiate PrEP after the Week 39 study visit, PrEP will not be provided at the study site; rather the participant will be linked to local PrEP services.

For participants in the U.S., a choice of either Descovy® (FTC/TAF) or Truvada® (FTC/TDF) will be offered at the enrollment visit. Participants may choose to switch PrEP study agents during follow-up. Site staff must document in eCRFs which PrEP study product a participant initiates and if study product is switched during follow-up.

For participants enrolled at the site in Brazil, only Truvada® (FTC/TDF) will be offered as PrEP study product as noted in Section 5.1.

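### Section 6.4.2 stops voluntary PrEP restarts at Week 39, while Section 5.2 allows them through Week 65 for those who first started on site by Week 39

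*Combined protocol and SAP*

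**What the plan says.** Section 5.2 (Study Product Administration, PrEP) has separate deadlines for two acts. First initiation is open through the Week 39 visit. For restarting, the rule is: "A participant can reinitiate PrEP after discontinuation up to, and including, Week 65 of study participation". Study supply at restart depends on when the participant first started: if she "had originally initiated PrEP use at site by Week 39 of study participation, the participant is eligible to receive PrEP provided by the study". Someone never supplied at the site by Week 39 is linked to local PrEP instead.

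Section 6.4.2 has a single deadline for both acts: "Participants who decline PrEP can begin (or reinitiate) PrEP at any time up to and including their Week 39 visit unless contraindicated". Among the situations it covers, it says: "This includes product being held due to a clinical event or because a participant declines either PrEP or GAHT during follow-up". It then defines the act: "Re-initiation is defined as restarting study product use after 30 or more days off study product".

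Section 6.4.1 defines stopping by the same interval: "Discontinuation is defined as not using study product for 30 or more days, independently of the rational for study product discontinuation".

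Section 3.1 mentions Week 39 only in connection with a first start, and its route to local services is for this case: "If a participant has not been provided PrEP on study by Week 39 and decides to initiate PrEP after the Week 39 study visit".

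**The concern.** Two operative sections give different deadlines for the same act by the same person. Section 6.4.2 is the one that site staff must open when handling a restart, because it lists the tests whose results are needed before PrEP is dispensed again. Staff who take its Week 39 sentence as the limit would turn away participants whom Section 5.2 makes eligible.

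A participant refused in this way has no specific route to PrEP. The explicit linkage in Sections 3.1 and 5.2 covers only people not supplied on site by Week 39. She would depend on a consultation with the Clinical Management Committee (CMC) that Section 6.4.2 makes optional, on general referral by her peer navigator (available to both arms after month 6), or on the linkage arranged before the Week 78 termination visit.

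The disputed weeks also fall in the part of follow-up that Sections 1.2 and 3.1 reserve for studying persistence, and persistence belongs to a primary objective (Section 2.1). Refused restarts could lower it, and different readings across the five sites would make it inconsistent.

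**Working it through.** The plan gives no figure to reproduce here. The check is a comparison of text, followed by simple bounds.

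**Step 1: do both rules reach the same person?** Take a participant who starts PrEP on site at enrollment, stops by choice at Week 26 and asks to restart at Week 52.

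- Under 6.4.1 she has discontinued, since she has been off product for more than 30 days and the reason is irrelevant.
- Under 5.2 she may restart, because Week 52 is before Week 65, and she is supplied on site, because she first started before Week 39.
- Under 6.4.2 she has declined PrEP during follow-up and her restart meets that section's definition of re-initiation, but Week 52 is past Week 39.

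She is eligible under one section and not under the other. The cutoffs differ by 65 − 39 = 26 weeks.

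**Step 2: can a narrower meaning of declining remove the conflict?** If it meant never having accepted PrEP, the parenthetical about reinitiating would be empty, because a re-initiator must already have started. Section 6.4.2 also speaks of declining during follow-up, and it gives a separate lipid-testing rule for those reinitiating. The narrow meaning fails. Restarts after a clinical hold are a different matter: the Week 39 sentence names people who decline, so it does not clearly bind them.

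**Step 3: which rule was intended?** Sections 3.1 and 5.2 tie Week 39 to first starts. Appendix Ia schedules PrEP provision through Week 65, which fits 5.2 but would also be needed for continuing users, so it does not decide the point.

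**Step 4: upper bounds for one refused participant.** Inputs are the Table 6 target days: Week 39 = 273, Week 52 = 365, Week 65 = 456, Week 78 = 547. Section 8.6.1 does not state the denominator of the persistence score, so I assume all six follow-up visits (Weeks 13 to 78).

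| Refused at | Days without study PrEP | Visits at stake | Share of own score |
|---|---|---|---|
| Soon after Week 39 (e.g. an interim visit) | 547 − 273 = 274 | 3 (Weeks 52, 65, 78) | 3/6 = 50 points |
| Week 52 | 547 − 365 = 182 | 2 (Weeks 65, 78) | 2/6 = 33 points |
| Week 65 | 547 − 456 = 91 | 1 (Week 78) | 1/6 = 17 points |

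If only visits after initiation count, as the drug-level endpoint in Section 8.2.1 might suggest, the three-visit case depends on when she started: 3/6 = 50 points (enrollment), 3/5 = 60 (Week 13), 3/4 = 75 (Week 26) or 3/3 = 100 (Week 39). A Week 39 starter cannot re-initiate before Day 273 + 30 = 303, so her maximum is 547 − 303 = 244 days, although all three later visits are still at stake.

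**Step 5: effect on the trial summary.** One percent of enrollees is 0.01 × 310 = 3.1 people. With six visits in the denominator, each 1% affected lowers overall mean persistence by at most 1% × 1/6 = 0.17 to 1% × 3/6 = 0.50 points. The change in the arm contrast is the difference between arms in the share affected, times 1/6 to 3/6. It is zero if the shares are equal.

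**The case against.** The strongest reply is that the two sections can be read together. Section 6.4.2 is permissive: it says what decliners can do through Week 39 and does not expressly bar later restarts. Section 5.2 then governs Weeks 39 to 65 and admits only prior on-site starters. Section 5.2 is also the more specific rule, the CMC is available for advice, and the Study Specific Procedures Manual, which is not part of this document, may give sites clear instructions.

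This does not remove the conflict. Sections 3.1 and 5.2 use essentially the same formula about the Week 39 visit as a firm limit on first starts, so a site has good reason to read it as a limit in 6.4.2 as well. Consultation is optional, and a site that sees a clear cutoff has no prompt to ask. A manual should not have to settle a contradiction within the protocol.

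The objections to the size carry more weight:

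- The Week 39 visit may take place as late as Day 336, which leaves at most 547 − 336 = 211 days.
- Section 6.7 describes dried-blood-spot drug levels as averages over the preceding months. A restart at Day 303 leaves 365 − 303 = 62 days to the Week 52 target, so protective levels at that visit are not assured even with supply.
- After Week 26 both arms receive the same package (Section 3.1), and nothing in the document suggests that a misreading would act differently by arm.

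The figures are therefore ceilings for one hypothetical participant and do not estimate the effect on the trial.

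**Conclusion.** The inconsistency is real, and its severity is minor. For participants who started on site by Week 39 and stopped by choice, the protocol gives two re-initiation cutoffs 26 weeks apart and does not say which governs. Confidence in that reading is high.

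The consequence is less certain. It requires a site to follow 6.4.2, a participant to ask for a restart after Week 39, and that participant not to obtain PrEP elsewhere. How many would meet these conditions cannot be estimated from the document. Any effect would fall on individual access to study PrEP and on the level of persistence. The comparisons used to power the study, Week 26 uptake and adherence, are unaffected, as are the sample size and time to first discontinuation.

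**What to change.** Reword the PrEP sentence in Section 6.4.2 to match Section 5.2: first initiation up to and including Week 39; re-initiation up to and including Week 65 for participants who first initiated PrEP on site by Week 39. The tests required before dispensing stay as they are. The cost is one clause, issued by clarification memo or letter of amendment. It changes no sample size, endpoint or visit schedule.
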